10.2.9. Day 183 (Week 26 \pm 1 day) Visit of the Blinded Extension

This visit will be performed for safety purposes. The following assessments will be performed at the Week 26 visit of the optional blinded extension:

- Vital signs: body temperature, blood pressure and heart rate
- 12-lead ECG
- Review study drug accountability and compliance
- Suicidality assessment using the C-SSRS
- Record concomitant therapy
- Record AEs/SAEs

10.2.10. Visits Every 12 Weeks of the Blinded Extension

Patients will continue in the optional Blinded Extension period at least until the last patient reaches Extension Week 48 (nominal Week 72). After the last patient reaches Week 72, patients may continue on blinded therapy until a long-term safety study is available. The following assessments will be performed every 12 weeks of the optional blinded extension, if indicated:

- Blood/urine sampling for the following laboratory tests:
 - Hematology: RBC count, total and differential WBC count (basophils, eosinophils, lymphocytes, monocytes, and neutrophils), platelet count, hemoglobin, hematocrit, MCV, MCH, and MCHC
- Note: All total WBC and differential WBC counts will be blinded during the study.

- Blood chemistry: sodium, potassium, chloride, calcium, magnesium, phosphate, blood urea nitrogen, random glucose, albumin, alkaline phosphatase, creatinine, SGPT/ALT, SGOT/AST, GGT, amylase, total bilirubin, conjugated bilirubin,. Abnormal laboratory parameters inconsistent with clinical presentation of MS or suspicious of underlying medical condition should be repeated for accuracy. If an increase of amylase above the clinically notable value (≥ 300 U/L) is observed at any post randomization visit, lipase should be tested to determine the origin of elevated amylase (pancreatic versus extra pancreatic)
- Urine beta-hCG (females of childbearing potential only). If the urine pregnancy test is positive, do not dose and confirm with a serum pregnancy test.
- Vital signs: body temperature, blood pressure and heart rate
- 12-lead ECG
- Dispense study drug and patient diary
- Review study drug accountability and compliance
- EDSS and neurological examination
- MSFC AND LCLA
- Pulmonary function tests including FEV₁ and FVC measurements
- Suicidality assessment using the C-SSRS
- Record concomitant therapy
- Record AEs/SAEs

MRI assessments during the blinded extension:

- Brain MRI at approximately Weeks 48 and 72
- After Week 72, brain MRI will be performed annually

10.2.11. End of Study Visit of the Blinded Extension

When the last active patient who entered the optional blinded extension period has reached at least Week 72 and a long-term safety study is available, the End of Study assessments will be performed at the next scheduled visit. The following assessments will be performed:

- Blood/urine sampling for the following laboratory tests:
 - Hematology: RBC count, total and differential WBC count (basophils, eosinophils, lymphocytes, monocytes, and neutrophils), platelet count, hemoglobin, hematocrit, MCV, MCH, and MCHC
Note: All total WBC and differential WBC counts will be blinded during the study.
 - Blood chemistry: sodium, potassium, chloride, calcium, magnesium, phosphate, blood urea nitrogen, random glucose, albumin, alkaline phosphatase, creatinine,

SGPT/ALT, SGOT/AST, GGT, amylase, total bilirubin, conjugated bilirubin,. Abnormal laboratory parameters inconsistent with clinical presentation of MS or suspicious of underlying medical condition should be repeated for accuracy. If an increase of amylase above the clinically notable value (≥ 300 U/L) is observed at any post randomization visit, lipase should be tested to determine the origin of elevated amylase (pancreatic versus extra pancreatic)

- Urine beta-hCG (females of childbearing potential only). If the urine pregnancy test is positive, do not dose and confirm with a serum pregnancy test.
- Coagulation panel: prothrombin time (PT) and partial thromboplastin time (PTT)
- sTSH
- [REDACTED]
- [REDACTED]
- Complete physical examination: including evaluation of heart, lung, head and neck, abdominal, neurological, skin, and extremities
- Weight
- Vital signs: body temperature, blood pressure and heart rate
- 12-lead ECG
- Review study drug accountability and compliance
- Brain MRI (if End of Study corresponds to a scheduled MRI visit)
- EDSS and neurological examination
- MSFC AND LCLA
- MSQOL-54
- Pulmonary function tests including FEV₁ and FVC measurements
- OCT evaluation
- Dermatological examination
- Suicidality assessment using the C-SSRS
- Record concomitant therapy
- Record AEs/SAEs

Patients will be scheduled for a follow-up visit 4 weeks (± 5 days) after last dose.

10.3. Part B Treatment Period

Part B will commence after the DMC reviews the Part A interim analysis data and performs a thorough safety review. Patients dosed in Part A will be ineligible for participation in Part B.

10.3.1. Visit 1 (Baseline/Month 1)

Eligible patients will be randomized to treatment group on Visit 1.

The following assessments will be performed at the Visit 1 (Baseline/Month 1):

- Review of inclusion/exclusion criteria
- An interim medical history will be performed to complete the screening medical history. Medical events that occur between screening and first dose will be recorded as medical history
- Blood/urine sampling for the following laboratory tests:
 - Hematology: RBC count, total and differential WBC count (basophils, eosinophils, lymphocytes, monocytes, and neutrophils), platelet count, hemoglobin, hematocrit, MCV, MCH, and MCHC
Note: All total WBC and differential WBC counts will be blinded during the study.
 - Blood chemistry: sodium, potassium, chloride, calcium, magnesium, phosphate, blood urea nitrogen, random glucose, albumin, alkaline phosphatase, creatinine, SGPT/ALT, SGOT/AST, GGT, amylase, total bilirubin, conjugated bilirubin, hemoglobin A1c, and total cholesterol, triglycerides, high-density lipoprotein (HDL), and low-density lipoprotein (LDL).
 - Urinalysis: leukocytes, specific gravity, bilirubin, blood, glucose, ketones, pH, protein, and urobilinogen.
 - Urine beta-hCG (females of childbearing potential only). If the urine pregnancy test is positive, do not dose and confirm with a serum pregnancy test.
 - Standard PK sampling: PK sample is to be taken prior to dose administration
 - 
- Weight
- Vital signs: body temperature, blood pressure and heart rate. The special first dose monitoring procedures must be performed (see below and Guidelines for Monitoring Patients Taking Their First Dose in [Section 10.2.1.1](#))
- 12-lead ECG. The special first dose monitoring procedures must be performed (see below and Guidelines for Monitoring Patients Taking Their First Dose in [Section 10.2.1.1](#))
- Randomization
- Dispense study drug (with titration kit) and patient diary, and administer first dose of study drug at the site
- MSFC AND LCLA
- MSQOL-54

- Suicidality assessment using the C-SSRS
- Record concomitant therapy
- Record AEs/SAEs

On Day 1 of treatment, careful cardiac monitoring of the patients is required. The first dose of RPC1063 should be administered in a setting in which resources to appropriately manage symptomatic bradycardia are available. A member of the Investigator team should be available to monitor the patient for the 6 hours monitoring period and will need to report any abnormalities to the treating neurologist. Atropine or Epinephrine need to be readily available to the site personnel.

Additional observation should be instituted until the finding has resolved in the following situations:

- The heart rate 6 hours post-dose is < 45 bpm
- The heart rate 6 hours post-dose is at the lowest value post-dose (suggesting that the maximum PD effect on the heart may not have occurred)
- The ECG 6 hours post-dose shows new onset second degree or higher AV block
- The ECG 6 hours post-dose shows a prolonged QTcF interval (>450 msec males, >470 msec females).

Should post-dose symptomatic bradycardia occur, initiate appropriate management, begin continuous ECG monitoring, and continue observation until the symptoms have resolved.

Should a patient require pharmacologic intervention for symptomatic bradycardia, continuous overnight ECG monitoring in a medical facility should be instituted, and the first dose monitoring strategy should be repeated at Day 5 if any cardiac safety issues were observed on Day 1.

Refer to Guidelines for Monitoring Patients Taking Their First Dose in [Section 10.2.1.1](#) for further details.

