10.2.1.1. Guidelines for Monitoring Patients Taking Their First Dose of RCP1063

On Day 1 of treatment, careful cardiac monitoring of the patients is required. The treating physician is responsible for monitoring the patient following the first intake of the study drug, as well as managing bradycardia symptoms should they occur. He or she must review the baseline predose ECG, vital signs during the 6-hour monitoring period, post-dose ECG, and assess discharge status at 6 hours after dosing. Baseline predose ECG should be provided by the site and be available for comparison to the postdose ECG in order to determine if criteria requiring extended monitoring are met. In addition, continuous Holter monitoring will be performed beginning 15 minutes predose and for 24 hours after dose administration. Further details on ECG and Holter monitoring procedures are provided in the Holter Manual.

Heart rate, blood pressure, and other vital signs will be measured before the first dose of study drug, then every hour for at least 6 hours thereafter (by the treating physician or an assisting nurse). Blood pressure and heart rate will be measured in the supine position and then the standing position at each time point. When obtaining the predose heart rate before the first dose, the patient should be allowed to rest in the supine position for 10 to 15 minutes before taking the heart rate. The supine heart rate and blood pressure measurements should be repeated 2 additional times to produce 3 readings for both heart rate and blood pressure (before the first dose of study drug only). The lowest predose value of supine heart rate and blood pressure (based on systolic blood pressure) will be recorded in the case report form and should be used for comparison to the postdose values. Orthostatic blood pressure will then be measured once with the patient in the standing position (after standing for 2 minutes) before the first dose of study drug.

Patients should receive the first dose of study drug in a fasted condition before 12:00 pm (noon) in the clinic. The first dose of RPC1063 should be administered in a setting in which resources to appropriately manage symptomatic bradycardia are available. A member of the Investigator team

should be available to monitor the patient for the 6 hours monitoring period and will need to report any abnormalities to the treating neurologist. Atropine needs to be readily available to the site personnel.

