Additional extended monitoring should be instituted until the finding has resolved in the following situations:

- The heart rate 6 hours post-dose is < 45 bpm
- The heart rate 6 hours post-dose is at the lowest value post-dose (suggesting that the maximum PD effect on the heart may not have occurred)
- The ECG 6 hours post-dose shows new onset second degree or higher AV block
- The ECG 6 hours post-dose shows a prolonged QTcF interval (>450 msec males, >470 msec females).

Should post-dose symptomatic bradycardia occur, the treating neurologist should be notified and he or she should initiate appropriate management, begin continuous ECG monitoring, and continue observation until the symptoms have resolved.

Should a patient require pharmacologic intervention for symptomatic bradycardia, continuous overnight ECG monitoring in a medical facility should be instituted, and the first dose monitoring strategy should be repeated the following day (Day 2). The first dose monitoring strategy should also be repeated at Day 5 if any cardiac safety issues were observed on Day 1.

Patients should have written instruction on when to return to clinic and a 24-hour contact phone number to call in the event of any new or warranted symptoms (e.g., chest pain, dizziness, palpitations, syncope, nausea, vomiting). Patients should be instructed not to drive on the same day after the first dose of study drug administration.

First dose monitoring procedures will also be followed at the Week 24 visit in Part A for patients who elect to continue in the blinded extension study, or for any patient who resumes treatment after missing more than 7 consecutive doses.

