- c. Hepatotoxicity. Fingolimod caused frequent, reversible liver enzyme elevations greater than 3-fold above the upper limit of normal in up to 12% of patients; this was a significant cause of cessation of therapy. In this study, clinical chemistry analyses to assess LFTs will be performed. Every patient whose LFTs are abnormal will be followed until values return to baseline.
- d. Macular edema. Instances of serious macular edema were reported in fingolimod renal transplant studies, and a 0.8% incidence was reported as an SAE in fingolimod (1.25 mg dose) MS clinical studies. Nonclinical studies with RPC1063 have not revealed eye-related toxicities. In this study, measurement of central foveal thickness by OCT will be performed in all patients. For patients

with abnormal OCT findings or with visual signs or symptoms of macular edema, a general ophthalmologic examination including eye history, visual acuity, and dilated ophthalmoscopy will also be performed. Every patient whose ophthalmic evaluations reveal abnormalities will be followed until values return to baseline or no further improvement is expected by the investigator (based on a follow-up period of not less than 3 months).

Overall, the following procedures should be followed:

- Vital signs will be assessed in supine and standing position at every visit. A sudden, significant fall in blood pressure (> 20 mmHg) between 2 and 5 minutes after standing from the supine position will be interpreted as an orthostatic hypotension and will be documented in the patient chart and eCRF.
- Patients will be closely monitored in the clinic after their first dose of the initial dose titration regimen for a period of 6 hours after treatment. ECGs will occur predose and at Hour 6 following dosing, with more frequent assessments as clinically indicated; vital signs, including orthostatic blood pressure assessment, will be assessed predose and then hourly for 6 hours following dosing. See the monitoring guidelines in [Section 10.2.1.1](#) for further details.
- Clinicians should be particularly mindful of patients who have a low pulse at baseline (spontaneously or through drug induced β -receptor blockade), prior to administration of the study drug. Atropine IV is recommended as the first line treatment of bradycardia, up to a maximum daily dose of 3 mg. Furthermore, the common guidelines for treatment of bradycardia (e.g. Advanced Cardiac Life Support-ACLS guidelines) should be followed as appropriate:

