 - In case of clinical symptoms or hypotension, administration of atropine 1 mg, repeated administration in 3-5 minutes.
 - If heart rate and/or blood pressure remains unresponsive, consider administration of dopamine drip 5-20 μ g/kg/min or epinephrine drip 2-10 μ g/min.
 - Performance of transcutaneous pacing may also be considered
 - In the setting of decreased blood pressure, isoproterenol should be avoided or used with caution.
- Any condition that might affect the outcome of pulmonary function testing (FEV₁ and FVC) including infection, respiratory symptoms, occupational exposures (including asbestos) and cigarette smoking, needs to be collected before every PFT testing and transcribed to the pulmonary function tests eCRF page. If patients have decline in PFT values (FEV₁ and/or FVC) below 50% of the predicted values, treatment should be discontinued. If a patient discontinues due to respiratory AE, the Investigator should ensure that the patient has adequate evaluations as clinically indicated by a pulmonologist (consider pulmonary function tests, chest X-ray or high resolution computed tomography, based on findings of the other exams) at the time of the AE. For patients with pulmonary nodules, lung biopsy should be considered (Cryptococcus pneumonia and pulmonary TB have been reported with fingolimod). Further evaluations will be conducted until such time as resolution is confirmed or no

CONFIDENTIAL

The information contained herein may not be used, disclosed, or published without the written consent of Receptos.

further improvement is expected by the investigator (based on a follow-up period of not less than 3 months).

- If patients have elevations in the LFTs (SGPT/ALT or/and SGOT/AST) greater than 3 times the ULN, a retest must be performed within 14 days. Upon confirmation of the abnormality, retests should be performed weekly until the elevated LFT decreases to below 3 times the ULN. If the LFT increase is confirmed to be above 5 times the ULN the study medication must be permanently discontinued.

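### Section 10.3.1 restates the Part B first-dose cardiac rules in a way that does not match 10.2.1.1 or 12.4: it lets epinephrine stand in for atropine, omits the Day 2 repeat and blurs the scope of the Day 5 repeat

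*Protocol*

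**What the plan says.** The general first-dose guideline is protocol section 10.2.1.1. On the rescue drug it states "Atropine needs to be readily available to the site personnel". For a patient who needs drug treatment for symptomatic bradycardia it asks for overnight ECG monitoring in a medical facility and then says that "the first dose monitoring strategy should be repeated the following day (Day 2"). A separate sentence adds a Day 5 repeat for any patient who had a cardiac safety issue on Day 1.

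Section 10.3.1 (Visit 1, Part B) restates these rules. On the rescue drug it states "Atropine or Epinephrine need to be readily available to the site personnel". For drug-treated patients it keeps the overnight ECG and then, in the same sentence, says that "the first dose monitoring strategy should be repeated at Day 5 if any cardiac safety issues were observed on Day 1". It does not mention Day 2. It refers to 10.2.1.1 three times: under vital signs, under the 12-lead ECG, and in its closing line.

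Section 12.4 is not limited to either part. It says "Atropine IV is recommended as the first line treatment of bradycardia", and its treatment steps begin: "In case of clinical symptoms or hypotension, administration of atropine 1 mg, repeated administration in 3-5 minutes". The next step is "If heart rate and/or blood pressure remains unresponsive, consider administration of dopamine drip" at a stated dose, "or epinephrine drip 2-10" μg/min.

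**The concern.** The text in 10.3.1 is what a Part B site has in front of it on the dosing day. If it allows either drug, a site can hold epinephrine alone, satisfy that sentence, and be unable to give the first treatment step of 12.4. If it omits the Day 2 repeat, a patient who was drug-treated for symptomatic bradycardia on Day 1 could take the next dose without repeat first-dose monitoring. If the Day 5 repeat is read as applying only to drug-treated patients, others with a Day 1 cardiac finding could miss it.

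Part B may also enrol patients with stable pre-existing cardiac disease, whom 9.4.3.2 describes as possibly at higher risk of cardiac events. Part A excluded clinically relevant cardiovascular conditions.

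**Working it through.** The plan states no figure on this point, so the check is a comparison of texts followed by a count of monitoring sessions.

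| Item | 10.2.1.1 | 10.3.1 (Part B) | 12.4 |
|---|---|---|---|
| Rescue drug | Atropine | Atropine or epinephrine | Atropine first; dopamine or epinephrine drip if unresponsive |
| Four Hour 6 criteria for extended observation | Listed | Same four listed | Refers to 10.2.1.1 |
| Drug-treated symptomatic bradycardia: overnight ECG | Yes | Yes | – |
| Drug-treated: repeat on Day 2 | Yes | Absent | – |
| Day 5 repeat | Separate sentence, any Day 1 cardiac safety issue | Joined to the drug-treated sentence | – |

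**Rescue drug.** A site that stocks atropine satisfies all three sections. A site that stocks only epinephrine satisfies the quoted sentence of 10.3.1, but not 10.2.1.1, and it cannot deliver the first step of 12.4.

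**Drug-treated patients, if a site follows 10.3.1 alone.**
- Repeat sessions under 10.2.1.1: Day 2 and Day 5 = 2.
- Repeat sessions under 10.3.1: Day 5 = 1.
- Loss: 2 − 1 = 1 session, on Day 2.
- Table 7 gives 0.25 mg on Days 1 to 4, so the Day 2 dose equals the Day 1 dose (0.25/0.25 = 1).

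**Patients with another Day 1 cardiac issue, if a site follows 10.3.1 alone.**
- Broad reading of the Day 5 sentence: one repeat at Day 5, as in 10.2.1.1; loss 0.
- Narrow reading (drug-treated patients only): no repeat; loss 1. The next scheduled visit in Table 3 is Day 15 ± 1, which is 14 − 1 = 13 to 16 − 1 = 15 days after the first dose.

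**Which reading of the Day 5 sentence is better?** It carries its own condition, that a cardiac safety issue was observed on Day 1. Anyone drug-treated for symptomatic bradycardia after the first dose has already met that condition, so the narrow reading makes it redundant. The broad reading gives it work to do and matches 10.2.1.1. The sentence is ambiguous, but the broad reading is the more natural.

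**Do the fuller rules still apply?** Yes. Besides the three references within 10.3.1:
- Section 9.4.3.2 sends Part B patients with stable cardiac disease to 10.2.1.1 unless the cardiologist wants more intensive monitoring.
- Section 12.4 refers to 10.2.1.1 for first-dose monitoring.
- Table 3 footnote 8 leads to Table 5, whose footnote 5 points to 10.2.1.1 for discharge criteria.

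**Is the difference deliberate?** Section 8.2.2 allows Part B first-dose monitoring to be modified by amendment after Part A results, but no text links that provision to these three differences. Where a Part B difference is intended, Table 5 footnote 4 states it (no Holter monitoring).

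**The case against.** The strongest reply is that 10.3.1 is a summary, not a competing rule. It tells the reader to follow both its own text and 10.2.1.1, and it ends by sending the reader there for detail. Leaving out Day 2 is then abbreviation. The same paragraph also requires a setting equipped to manage symptomatic bradycardia; since 12.4 makes atropine first line, an epinephrine-only site arguably fails 10.3.1 read as a whole.

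Much of this stands. The cross-references keep the fuller rules in force, which limits the concern to a site that does not follow them. The reply does not remove the mismatch. Neither section says which text prevails. The sentence about an equipped setting also appears in 10.2.1.1, beside the atropine requirement, so it was not meant to replace a named drug.

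A reader might infer a larger problem in three ways that the documents do not support:
- *Three doses (Days 2, 3 and 4) go without repeat monitoring.* Section 10.2.1.1 schedules no repeat on Days 3 and 4 either, so only Day 2 is lost.
- *Patients with Day 1 findings go unwatched for about two weeks while the dose doubles on Day 5 and, in the 1 mg arm, reaches four times the starting dose on Day 8.* That needs the weaker reading of the Day 5 sentence. Even then, 10.3.1 keeps patients with the listed Hour 6 findings, or with symptomatic bradycardia, under observation until resolution. Section 7.2.4 reports negligible further heart-rate reduction after Day 4 of titration despite higher doses, so dose multiples do not measure the risk.
- *Phase 1 gives the event rate.* Grade 2 cardiac events occurred in 4 of 66 subjects given RPC1063 (6.1%), but at 1.5 or 3 mg. These are 1.5/0.25 = 6 to 3/0.25 = 12 times the Part B starting dose, and the events are reported as resolving without intervention. They say little about a 0.25 mg first dose.

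**Conclusion.** The concern holds as a minor inconsistency in an operative safety instruction. The main mismatch is the rescue drug: 10.3.1 accepts epinephrine as an alternative where 10.2.1.1 requires atropine and 12.4 makes it the first step. The missing Day 2 repeat and the ambiguous Day 5 sentence are secondary.

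The consequence assumes a site that acts on 10.3.1 without following its references. There, a site could lack atropine, and each drug-treated patient would lose one repeat monitoring session, at an unchanged dose. The number of patients cannot be derived, because the documents give no rate of drug-treated bradycardia at 0.25 mg. No estimand, power calculation or analysis is affected.

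**What to change.** In 10.3.1, require atropine to be on hand, with epinephrine in addition. After the overnight ECG clause, restore two separate sentences in line with 10.2.1.1: repeat first-dose monitoring on Day 2 after drug treatment for symptomatic bradycardia, and repeat it at Day 5 after any Day 1 cardiac safety issue, drug-treated or not.

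A simpler alternative is to delete the duplicated text and refer to 10.2.1.1, stating that Holter monitoring does not apply in Part B. If any difference is intended for Part B, say so expressly.

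The cost is wording in one section. Since 10.2.1.1 already requires these repeats, the change adds no required visits and leaves the visit schedule, sample size and analysis as they are.
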